Timing: *Pre-discharge Environmental Modification Intervention.* Using standardized assessment and manualized procedures, environmental modifications will be installed before discharge. The intervention (not reimbursable) will be provided at no cost to the participant. *Post-discharge Activity and Participation Intervention.* On completion of T1b phone assessment, the participant will receive visits 2–5 over an 8-week period. Interventions will progress in complexity from daily activities to community participation based on the participant's goals. A booster session will be provided at 4 and 5 months after intervention over the phone; participants may request a home visit.

Attention Control Group

The control group will experience the same effects of time and attention in the home but no effect on the outcome of interest.⁷⁴ Because this study examines the efficacy of a new intervention, there is no opportunity for a usual care arm with dose equivalency. Because 75% of stroke survivors and 78% of caregivers report that their informational needs were not met in the hospital,⁷⁵ we developed and piloted a tailored stroke

education program for AC. An OT practitioner will deliver the program in accordance with “Evidence-Based Educational Guidelines for Stroke Survivors after Discharge Home.”⁷⁶ Topic order is determined by participants. Four 75-minute sessions will be provided. Topics include stroke symptoms, risk factors and preventing stroke recurrence, nutrition, managing emotions, sleep, fatigue, pain, social support, and sexuality. Written materials from the National Stroke Association and the American Stroke Association are provided. Environmental barriers will not be addressed in the educational sessions.

Follow-up Period for All Participants

Stroke and caregivers: Home visits T2 (immediately after intervention), T3 (6 months after stroke), and T4 (12 months after stroke). The follow-up activity, participation, and process assessments will be conducted in the home. All follow-up assessments will be completed by a blinded rater who did not conduct the T1 evaluation, as new home modifications could reveal group assignment. Distal time points will explore the permanency of any treatment effect on participation. If the participant is not available for in-home assessment, the primary endpoint will be collected by phone. Falls and healthcare utilization are collected **monthly** by phone (using an automated system).

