In-Home Occupational Performance Evaluation (I-HOPE). The I-HOPE will be used to measure current activity patterns of participants, identify activities that are difficult but important to them, and identify the environmental barriers that influence those activities (person–environment fit). The I-HOPE is a multi-step assessment that evaluates the performance of older adults doing 42 activities in the home. Using labeled pictures of each home activity (e.g., washing dishes, getting in and out of bed), older adults identify activities difficult for them to perform and self-rate their performance and satisfaction with performing each of the activities. A trained rater (e.g., OT interventionist) observes the older adult performing the activity and quantifies the person–environment fit (or misfit). The instrument yields four subscales: the activity subscale ($\alpha = 0.78$; 6 items); the performance subscale ($\alpha = 0.85$; 38 items); the satisfaction subscale ($\alpha = 0.77$; 8 items); and the environmental barrier subscale ($\alpha = 0.77$; 6 items). Intraclass correlation coefficients were calculated for the I-HOPE subscales on a sample of 10 participants, and scores ranged from 0.94 to 1.0 for raters.⁷⁷

Barthel Index (BI). The BI is a reliable and valid assessment that will be used to assess a person's ability to complete 10 ADLs (feeding, bathing, grooming, dressing, bowel control, bladder control, toileting, chair transfer, ambulation, and stair climbing) and the amount of assistance they need to complete these activities. We will use this information to examine changes in participants' functional performance in this study. There is excellent correlation and agreement for stroke patients between the FIM motor and 10-item Barthel at admission and discharge ($r \geq 0.92$; $ICC \geq 0.83$).⁷⁸

Stroke Impact Scale (SIS). The SIS is a health-related quality of life measure that quantifies the impact of stroke on a participant's life, via questionnaire. Fifty-nine items are measured across eight domains: strength, hand function, mobility, ADLs and instrumental activities of daily living (IADLs), emotion, memory, communication, and participation. Performance is self-reported based on the difficulty the participant

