For the secondary analyses of the change in SIS score at 1 year and the change in I-HOPE at 1 year, we will use the same approach as for the primary analysis because these two outcomes are also continuous. We have overall type I error control for testing the 1-year change in these three analyses at the design stage. The significance level for testing is 0.016. In addition to comparison of 1-year change, we will extend the model by including scores immediately after intervention and at 6 months to see whether the difference in outcomes is achieved at those time points. Depending on the form of time variable in the model, we will use appropriate regression coefficients or a linear combination of the regression coefficients to determine the difference in change of these scores between arms at certain time points. Interpretation of these results should be cautious because we do not have the type I error controlled for these analyses. Because it is possible that severity of functional impairment after stroke may impact response to treatment, we will analyze impact of functional impairment on response to treatment. We will examine functional impairment by group interaction to examine possible differential intervention effects of functional impairment on community participation and performance of daily activities.

Safety

To determine whether the intervention poses no greater risk than AC, we will examine the differences in numbers of falls and rehospitalizations between groups. The statistical models for count data will be used for analyses of these two outcomes. Using the number of falls as an example, we will fit a Poisson regression model (with overdispersion adjustment if necessary), in which a dummy variable for the intervention arm is used. The regression parameter estimate for this dummy variable is the log of rate ratio of falls for COMPASS versus control arm, and exponentiation of the regression parameter estimate is rate ratio. Using the parameter estimate and its standard error, we can construct a two-sided 95% CI for the rate ratio. We expect the confidence interval for rate ratio will include 1, indicating no significant difference in the fall rate between the two groups.

Process Outcomes

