Evaluate acceptability and feasibility to aid in the interpretability of the trial. COMPASS will have high acceptability (80% retention), high fidelity by therapists (95% of elements and 90% of dose delivered), low safety risk (no increased rate of falls or health care use compared with the AC group), and high adherence (80% of modifications in use) at 12 months. We will conduct between-group comparisons of process endpoints collected at each time point (time to first fall, number of injurious falls, health care utilization rate, dosage delivered, and adherence rate) using unpaired *t* tests or chi-square tests. We will compare the characteristics of patients who complete the assigned intervention with those who do not for differences in stroke severity and comorbidities. Descriptive statistics will be used for costs per participant and adherence.

Sample Size Calculations

The study is designed to have 80% of power to reject three null hypotheses of equal mean changes in the primary and secondary endpoints (RNLI, SIS, and I-HOPE) using a two-sided, two-sample, unequal-variance *t* test with overall type I error <0.05 . Three alternative mean changes (standard deviation [SD] of change) in intervention and control populations are 15.3 (SD 22.6) versus 1.3 (SD 23.4) for RNLI, 15.7 (SD 16.1) versus 5.6 (SD 9.1) for the SIS ADL domain, and 62.1 (SD 26.1) versus 46.2 (SD 18.8) for I-HOPE. With a 1:1 allocation ratio, 130 patients (65 in each group) are needed for the RNLI outcome, 84 are needed for the SIS outcome, and 100 are needed for the I-HOPE outcome. We will enroll 180 patients to account for a 30% attrition rate. This magnitude of between-group difference is considered clinically meaningful based on prior relevant literature and is achievable based on our pilot study. Sample size calculation includes correlation between baseline and follow-up measures and is based on analysis of change scores, which is equivalent in efficiency to the proposed analytic model. Based on the number of stroke patient participants, we will enroll an equivalent number of caregivers.

Strengths and Limitations

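### The 130/84/100 patients called needed do not follow from 80% power at the documented 0.016 level, and 30% attrition from 180 leaves 126, not 130

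*Combined protocol and SAP*

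**What the plan says.** Under Sample Size Calculations: "The study is designed to have 80% of power to reject three null hypotheses of equal mean changes". The test is a two-sided, two-sample, unequal-variance t test with 1:1 allocation and overall type I error below 0.05. The section gives mean changes and SDs of change for each endpoint, among them "15.3 (SD 22.6) versus 1.3 (SD 23.4) for RNLI" and "62.1 (SD 26.1) versus 46.2 (SD 18.8) for I-HOPE"; for the SIS ADL domain they are 15.7 (SD 16.1) against 5.6 (SD 9.1). It then concludes that "130 patients (65 in each group) are needed for the RNLI outcome, 84 are needed for the SIS outcome", and 100 for I-HOPE. The enrolment target follows: "We will enroll 180 patients to account for a 30% attrition rate".

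The per-test level is given elsewhere, under Secondary Analyses, for the three one-year comparisons: "The significance level for testing is 0.016".

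**The concern.** This section is the only justification of the sample size, and it supplies everything needed to repeat the calculation except the per-test alpha, which Secondary Analyses supplies. Three things do not fit together.

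- The stated numbers are larger than 80% power at 0.016 requires, by more than rounding explains.
- The attrition allowance does not return the number called needed.
- Power to reject three null hypotheses can be read as power for each test or as power for all three together, and the text does not say which.

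A reader therefore cannot tell which alpha and power produced 130/84/100. That affects whether the promised 80% is kept once attrition is taken off. The document also says the trial is meant to help design a phase III study, so these figures may be reused.

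**Working it through.** **Inputs** (Sample Size Calculations, except alpha)

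| | RNLI | SIS ADL | I-HOPE |
|---|---|---|---|
| Difference in mean change, d | 15.3 − 1.3 = 14.0 | 15.7 − 5.6 = 10.1 | 62.1 − 46.2 = 15.9 |
| SDs of change, s1 and s2 | 22.6, 23.4 | 16.1, 9.1 | 26.1, 18.8 |
| s1² + s2² | 1058.32 | 342.02 | 1034.65 |
| Stated total N (per arm) | 130 (65) | 84 (42) | 100 (50) |

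Alpha is 0.016 two-sided (Secondary Analyses). The SDs are of change, and the section says the baseline/follow-up correlation is already included, so no further variance reduction applies.

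**Method.** With n per arm, SE = √[(s1² + s2²)/n] and the noncentrality is d/SE. Degrees of freedom are Satterthwaite's, and power comes from the noncentral t distribution. The required n is the smallest that reaches the target.

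**Step 1: reproduce the stated numbers**

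| Two-sided alpha | Power | RNLI | SIS ADL | I-HOPE |
|---|---|---|---|---|
| 0.016 | 80% | 118 | 76 | 90 |
| 0.05/3 | 80% | 116 | 74 | 90 |
| 0.05 | 80% | 88 | 56 | 68 |
| 0.016 | 85% | 132 | 84 | 102 |
| **0.05/3** | **85%** | **130** | **84** | **100** |
| **0.01** | **80%** | **130** | **84** | **100** |

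The documented pair (0.016, 80%) does not return the stated numbers; they exceed it by 12, 8 and 10. With power held at 80%, a scan of alpha in steps of 0.0001 returns exactly 130/84/100 only from 0.0099 to 0.0103, so 0.016 is not a rounding of the level that fits. As a check, the normal approximation n = (2.409 + 0.842)²(s1² + s2²)/d² at 0.016 and 80% gives 57.1, 35.4 and 43.2 per arm. Rounded up, the totals are 116/72/88, also below the stated numbers.

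**Step 2: power at the stated numbers, alpha 0.016**

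- RNLI, 65 per arm: SE = √(1058.32/65) = 4.035; noncentrality 14.0/4.035 = 3.470; power 84.6%.
- SIS ADL, 42 per arm: SE = √(342.02/42) = 2.854; noncentrality 10.1/2.854 = 3.539; power 85.3%.
- I-HOPE, 50 per arm: SE = √(1034.65/50) = 4.549; noncentrality 15.9/4.549 = 3.495; power 84.8%.

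**Step 3: attrition**

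- 180 × 0.70 = 126 completers, against 130.
- 130/0.70 = 185.7, so 186 would have to be enrolled.
- 1 − 130/180 = 27.8%.
- 118/0.70 = 168.6, so 169 enrolled would suffice for 80% RNLI power at 0.016.

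**Step 4: power at 126 completers (63 per arm)**

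| Alpha | RNLI | SIS ADL | I-HOPE |
|---|---|---|---|
| 0.016 | 83.3% | 96.9% | 92.8% |
| 0.05/3 | 83.7% | 97.0% | 93.1% |
| 0.01 | 78.6% | 95.4% | 90.1% |

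These figures assume that all 126 are evaluable on every endpoint. That may not hold for I-HOPE. The follow-up section provides that "If the participant is not available for in-home assessment, the primary endpoint will be collected by phone", with no such promise for the others, and for I-HOPE a rater "observes the older adult performing the activity". The document gives no evaluable number, so here is a range at 0.016: 110 evaluable, 88.5%; 100, 84.8%; 90, 80.1%; 88, 79.1%.

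**Step 5: the joint reading.** If the 80% meant rejecting all three, 126 completers at 0.016 give 0.833 × 0.969 × 0.928 = 74.9% with independent endpoints. Independence is an assumption; positive correlation raises the figure. Sizing each endpoint separately points to the per-test reading.

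**The case against.** The strongest reply is that nothing is lost. The stated numbers exceed what 0.016 requires, RNLI power at 126 is still above 80%, and enrolment has closed. That is right as to consequence. It does not make the reported figures correct, and it says nothing about 126 against 130.

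A second reply is that alpha is not the item at fault. 0.016 is 0.05/3 cut to three decimals, and 85% power at 0.05/3 reproduces all three numbers; even at 0.016 a target of about 84.5% does so. On that view the slip is the 80%. This is plausible, and it would make the 0.01 scenario irrelevant. But the document states neither 85% nor 0.01, so it cannot settle which figure was misreported.

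Third, the version log attributes the change to 180 to retention rates, and the process outcomes set an 80% retention target, which would leave 180 × 0.80 = 144. The mixed model also keeps baseline data from those who drop out, so a t test on 126 completers is an approximation. All of that is fair, but the sentence in the plan says 30%, and 30% of 180 does not leave 130. The shortfall is small: 4 patients and 1.3 percentage points of RNLI power at 0.016 (84.6% to 83.3%).

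**Conclusion.** The point holds as an error in the reported design figures, not as a shortage of patients. At the documented 0.016 and 80% power the plan's inputs give 118/76/90, not 130/84/100, and 30% attrition from 180 gives 126, not 130. On the per-test reading at 0.016 the design keeps its promise, with RNLI the lowest at 83.3% with 126 completers.

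That reassurance rests on three assumptions: that 0.016 is the level that applies, that the 80% is per test, and that enough participants are evaluable on each endpoint (I-HOPE needs about 90). If 0.01 was the level used, RNLI power at 126 falls just under target, to 78.6%.

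**What to change.** 1. Report the alpha and power actually used for 130/84/100, taken from the record of the calculation and not chosen because they fit. If that record cannot be found, restate the required numbers as 118/76/90 for 80% power at 0.016 and say that they were recalculated.
2. State 126 expected completers at 30% attrition, with RNLI power of about 83% at 0.016. If about 28% was the attrition actually planned, say so instead; that is the rate that leaves 130.
3. Say that the 80% is per test. If power is also quoted for SIS ADL and I-HOPE, give the number expected to be evaluable on each.

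The cost is a few sentences. Enrolment, tests, the 0.016 level and data collection do not change.
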